3.7.1.3 Control Group

Since eligibility angiography (if indicated, see section 3.5.3.2 - Eligibility Coronary Angiography) and venography will be performed in all subjects prior to randomization, subjects ultimately randomized to the Control group will experience a procedure similar to the Treatment group to ensure that they will not be able to deduce their treatment assignment. In addition to the femoral arterial (for the eligibility angiography) and jugular venous punctures (for the eligibility venogram), subjects will undergo electrocardiographic and echocardiographic examinations similar to those performed during the CARILLON implant procedure. These subjects **will not** undergo placement of the CARILLON implant.

3.7.2 Study Subject Follow-up Categories

SCREEN-FAILURE → Subject consented but did not meet baseline eligibility criteria (including TEE, if applicable). No study discharge evaluations are necessary.

ENROLLED SCREEN-FAILURE → Subject consented, met all baseline eligibility criteria, but did not meet final angiographic eligibility. Implant was not attempted. Limited study discharge evaluations are necessary, but no follow-up visits are required.

PROCEDURAL SCREEN-FAILURE → Randomized to treatment group, but procedure discontinued before an implant attempt. Full study discharge evaluations are required and the subject is followed through 1-month.

NON-IMPLANTED → Randomized to treatment group, implant attempted, but not successful. Full study discharge evaluations are required and the subject is followed through 12-months.

IMPLANTED → Randomized to treatment group, device successfully implanted. Full study discharge evaluations are required and the subject is followed through 12-months.

CONTROL → Randomized to control group, implant not attempted. Full study discharge evaluations are required and the subject is followed through 12-months.

3.7.3 Discharge Evaluations

3.7.3.1 Randomized Subjects

Immediately following the index procedure, all randomized subjects will be observed overnight for complications related to the final eligibility assessments and/or procedure. This includes Procedural Screen Failures, Treatment subjects (non-implanted and implanted) and Control subjects.

Prior to hospital discharge, the following assessments will be performed:

- Physical examination
- Vital signs
- Abbreviated Echocardiogram (TTE) safety assessment
- Chest X-ray (PA and lateral) or cine fluoroscopy (for assessment of pulmonary congestion and assessment of implant integrity in implanted subjects)
- ECG (12-lead)
- Serum creatinine
- NT-BNP
- Cardiac enzymes: cardiac troponin (cTn)
Cardiac enzymes will be monitored 6-8 hours post procedure (or the following morning if procedure time was late in the day). If a clinically significant elevation in cardiac enzymes is noted then a repeat measurement should be undertaken for confirmation.
- CBC with differential, includes hemoglobin, hematocrit, platelets, and WBC
- Clinical assessments by the physician and other information to be evaluated and recorded as they occur including:
 - Concomitant medications
 - Adverse events

If the index procedure was discontinued before a CARILLON implant was attempted in a Treatment group subject, they are considered a Procedural Screen Failure and are followed through discharge and 1-month (safety assessment only), then exited from the study.

3.7.3.2 Enrolled Screen Failures

The following safety evaluations will be performed prior to discharge for subjects who were brought into the catheterization lab but **do not** meet final eligibility criteria or for any other reason device implant is not attempted:

- Vital signs
- ECG (12-lead)
- Serum creatinine
- Cardiac enzymes: cardiac troponin (cTn)

Enrolled screen failure subjects are followed through discharge and then exited from the study.

3.8 Study Follow-up Evaluations

Randomized subjects (Treatment and Control groups) will be required to complete all scheduled follow-up visits as outlined below:

- 1, 6 and 12 months

Subjects randomized to the Control group may be offered the CARILLON device once they have completed the 1-year protocol defined follow-up period (reference Section 3.8.7: Cross-Over Registry).

Reference Appendix E: Echocardiogram Protocol and Appendix F: Six Minute Walk Test for all study follow-up visits.

3.8.1 Follow-Up Schedule – One (1) Month

One (1) month (30 days \pm seven (7) days) after the index procedure, the study subject will return to the study site for follow-up evaluations. The evaluations at this visit will include:

- Physical examination
- Vital signs
- Echocardiogram (TTE)
Note: Study sites that have experience and necessary equipment may undertake exercise echocardiography in addition to the standard echocardiographic assessment required by the protocol.
- ECG (12-lead)
- Serum chemistries: sodium, potassium, chloride, glucose, BUN, creatinine, and NT-BNP
- Cardiac enzymes: cardiac troponin (cTn)
- CBC with differential, includes hemoglobin, hematocrit, platelets, and WBC
- Quality of Life questionnaires:

- KCCQ
- SF-12
- NYHA Classification assessment
- Functional assessment:
 - Six minute walk test
- Clinical assessments by the physician and other information to be evaluated and recorded as they occur including:
 - Concomitant medications
 - Adverse events

If the index procedure was discontinued before a CARILLON implant was attempted in a Treatment group subject, they are considered a Procedural Screen Failure and are followed through 1-month, then exited from the study.

3.8.2 Follow-up Schedule – Six (6) Months

Six (6) months (180 days \pm 14 days) after the index procedure, the study subject will return to the study site for follow-up evaluations. The evaluations at this visit will include:

- Physical examination
- Vital signs
- Echocardiogram (TTE)

Note: Study sites that have experience and necessary equipment may undertake exercise echocardiography in addition to the standard echocardiographic assessment required by the protocol.
- Chest X-ray (PA and lateral) or cine fluoroscopy (with device integrity assessment for implanted subjects)
- ECG (12-lead)
- Serum chemistries: sodium, potassium, chloride, glucose, BUN, creatinine, and NT-BNP
- CBC with differential, includes hemoglobin, hematocrit, platelets, and WBC
- Quality of Life questionnaires:
 - KCCQ
 - SF-12
- NYHA Classification assessment
- Functional assessment:
 - Six minute walk test
- Clinical assessments by the physician and other information to be evaluated and recorded as they occur including:

- Concomitant medications
- Adverse events

3.8.3 Follow-Up Schedule – Twelve (12) Months

Twelve (12) months (365 days \pm 30 days) after the index procedure, the study subject will return to the study site for follow-up evaluations. The evaluations at this visit will include:

- Physical examination
- Vital signs
- Echocardiogram (TTE)
 - Note: Study sites that have experience and necessary equipment may undertake exercise echocardiography in addition to the standard echocardiographic assessment required by the protocol.*
- Chest X-ray (PA and lateral) or cine fluoroscopy (with device integrity assessment for implanted subjects)
- ECG (12-lead)
- Serum chemistries: sodium, potassium, chloride, glucose, BUN, creatinine, and NT-BNP
- CBC with differential, includes hemoglobin, hematocrit, platelets, and WBC
- Quality of Life questionnaires:
 - KCCQ
 - SF-12
- NYHA Classification assessment
- Functional assessment:
 - Six minute walk test
- Clinical assessments by the physician and other information to be evaluated and recorded as they occur including:
 - Concomitant medications
 - Adverse events

3.8.4 Unscheduled Follow-Up Procedures and Data Requirements

In some circumstances, Investigators may need to see a subject in advance of the normal study schedule or a subject may return to the investigational site to report new or unresolved signs or symptoms. Such visits will be documented as unscheduled follow-up visits. No specific study evaluations are required to be performed at unscheduled visits, but adverse events will be documented and reported.

3.8.5 Study Exit

Upon completing the protocol defined follow-up, the subject will be exited from the study. Upon study completion, the study investigator should contact the patient's heart failure doctor to discuss their involvement in this study and ongoing medical treatment.

3.8.6 Subject Withdrawal

3.8.6.1 When and How to Withdraw Subjects

A subject may be withdrawn early from the study prior to study completion for several reasons, including but not limited to:

- Loss to follow-up
- Subject consent withdrawal
- Heart transplantation or other confounding intervention
- Physician discretion (for patient health reasons)

If a subject is withdrawn early from the study for any reason, the Cardiac Dimensions clinical study monitor must be notified by telephone, facsimile or e-mail. The Investigator or designee must document the reason for the termination of enrollment and advise Cardiac Dimension of situations that are not resolved.

A subject should not be considered lost to follow-up until three or more attempts have been made to contact the subject and all attempts have failed. One of these attempts should be a letter sent using certified mail with signature confirmation.

If a subject is withdrawn from the study early, the study investigator should contact the patient's heart failure doctor to discuss their involvement in this study and the ongoing medical treatment plan for the subject.

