3.8.6.3 Data Collection and Follow-up for Withdrawn Subjects

If a subject withdraws consent to participate in the study, attempts should be made to obtain permission to record survival data through the 1-year follow-up period.

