6.2 Study Analyses

The primary analyses will be conducted according to the principles of intent-to-treat. All subjects will be analyzed according to randomized group assignment, and subjects randomized to the Treatment group but who do not receive a permanent implant will be included. If any subject does not have endpoint data available (12-month data), the primary analysis will assume that data as missing and that subject's data will not be included in the primary analysis.

In addition, a series of supportive, sensitivity analyses will be performed to assess the robustness of the primary analysis results, including imputing the last value observed (last value carried forward) for all missing endpoint evaluations.

Additional subgroup analyses will be conducted for all primary and secondary endpoints on as-treated and per-protocol cohorts defined as:

- **As-treated:** All subjects who left clinic with the randomized therapy administered (i.e., randomized to Treatment group and received a permanent implant, or randomized to Control group)
- **Per-protocol:** All subjects who received randomized therapy, assessors remained blinded, and who did not receive alternative or confounding therapies (e.g., CRT therapy, transplant, stenting, etc.) through the primary endpoint timeframe of the study

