### 2.3.3. Protocol Deviations

On a case-by-case basis, all protocol deviations will be reviewed and will be classified as “minor” or “major” according to the possible impact expected on primary results.

Patients meeting at least one of the following major deviations may be excluded from the PP population:

- At least one eligibility criterion not fulfilled;
- Treatment different from the randomized group assignment;
- Unblinded assessor(s);
- Unblinded subject(s);
- Patient who received alternative or confounding therapies (e.g., CRT, transplant, stenting, etc.);
- Study Windows not respected

All protocol deviations other than those defined in this section will be considered as minor and will not lead to patient exclusion from the PP population.

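### Withdrawal for a confounding intervention, with no follow-up planned afterwards, can selectively remove subjects from the primary intent-to-treat analysis

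*Protocol*

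**What the plan says.** Protocol 3.8.6.1 introduces its withdrawal reasons with "A subject may be withdrawn early from the study prior to study completion for several reasons, including but not limited to", and the third reason is "Heart transplantation or other confounding intervention". The term is not defined. The section asks for notification, a documented reason and contact with the subject's heart failure doctor, but for no further outcome data.

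Protocol 3.8.6.3 is headed as covering withdrawn subjects in general, but it deals only with withdrawal of consent: "attempts should be made to obtain permission to record survival data through the 1-year follow-up period". Section 5.2.3 adds a termination assessment when a subject is removed for a severe adverse event. It does not give its content and plans nothing after it.

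For the analysis, Protocol 6.2 states "All subjects will be analyzed according to randomized group assignment" and adds that "subjects randomized to the Treatment group but who do not receive a permanent implant will be included". The same paragraph sets a complete-case rule: without 12-month data, the "primary analysis will assume that data as missing and that subject's data will not be included in the primary analysis". SAP 2.1.1 repeats that rule.

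In the analysis sections, confounding therapy matters only for the per-protocol set. Protocol 6.2 limits that set to subjects "who did not receive alternative or confounding therapies (e.g., CRT therapy, transplant, stenting, etc.) through the primary endpoint timeframe of the study", and Protocol 6.9 and SAP 2.3.2 follow it. SAP 2.3.3 lists as a major deviation "Patient who received alternative or confounding therapies (e.g., CRT, transplant, stenting, etc".

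**The concern.** Receiving cardiac resynchronization therapy (CRT), a stent or a transplant happens after randomization. It reflects how the patient is doing, and so possibly the arm. If data collection stops at that point, the subject has no 12-month echo and leaves the primary comparison. The 12-month walk distance and left ventricular volumes are lost as well, and later deaths and heart failure admissions have no stated route into the database. A per-protocol exclusion for confounding therapy is useful only if the same subjects remain evaluable under ITT. To the extent that they are withdrawn, the ITT versus per-protocol contrast cannot show what such therapy does to the result.

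Two features add to this. Under Protocol 4.1.4 the study coordinator and the implanting physician know the assignment, and 3.8.6.1 does not require a blinded person to decide on withdrawal. An undefined, optional rule could therefore be applied differently by site or by arm. Also, cardiac surgery or percutaneous coronary intervention (PCI) for device failure is a component of the major adverse event composite (3.2.2.1) and could itself be read as a confounding intervention. A Treatment subject with that event could be exited, with no stated follow-up for later events.

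**Working it through.** **1. The plan's own figure.** Inputs from Protocol 6.6: change of −2.4 ml in Control and −12.4 ml in Treatment, SD 13 ml, two-sided 0.05, 80% power, 3:1, t-test. With the noncentral t distribution, 54 + 18 = 72 subjects give 79.6% power and 57 + 19 = 76 give 81.8%. The stated 76 is reproduced, and this point does not change it.

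**2. Shift from selective loss.** Let completers have mean changes mT = −12.4 and mC = −2.4 ml. Let pT and pC be the shares withdrawn for a confounding intervention, and x the additional 12-month change those subjects would have shown, taken as equal in both arms.

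- Mean of a full arm: (1 − p)·m + p·(m + x) = m + p·x.
- Full ITT difference: −10 + (pT − pC)·x.
- Completer difference minus full difference: (pC − pT)·x.

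The documents give neither rates nor x, so the values below are assumptions. A negative shift favours the device.

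| pC | pT | x (ml) | Full ITT (ml) | Completers (ml) | Shift (ml) |
|---|---|---|---|---|---|
| 5% | 5% | −10 or +10 | −10.0 | −10.0 | 0 |
| 10% | 5% | −10 | −9.5 | −10.0 | −0.5 |
| 10% | 5% | +10 | −10.5 | −10.0 | +0.5 |
| 15% | 5% | −10 | −9.0 | −10.0 | −1.0 |
| 15% | 5% | +10 | −11.0 | −10.0 | +1.0 |
| 20% | 5% | −10 | −8.5 | −10.0 | −1.5 |
| 20% | 5% | +10 | −11.5 | −10.0 | +1.5 |

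The largest shift, 1.5 ml, is 15% of the 10 ml design difference. With equal shares and the same x in both arms the shift is zero.

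**3. Power.** Protocol 6.7 allows about 30% attrition: 120 × 0.70 = 84 evaluable, with 85.5% power at 63 + 21. If these withdrawals came on top, 35% total loss leaves 78 (58 + 20, 83.4%) and 40% leaves 72 (54 + 18, 79.6%). Selective loss is therefore the issue more than sample size.

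**4. How close ITT comes to per-protocol.** Protocol 6.6 allows up to 15% of Treatment subjects without an implant. That is 0.15 × 90 = 13.5, or about 13 subjects, who stay in ITT. The expected ITT difference is 0.85 × (−14.1 + 2.4) = −9.9 ml. For implanted subjects against Control it is −14.1 + 2.4 = −11.7 ml. The two comparisons remain distinct.

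**5. Scale for safety.** Control has 120 × 1/4 = 30 subjects, so one unrecorded Control death changes the 12-month rate by 1/30 = 3.3 percentage points. This is arithmetic, not a forecast.

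**The case against.** **The rule is permissive.** Section 3.8.6.1 says a subject may be withdrawn, and Section 3.8 requires randomized subjects to complete all scheduled visits. The sections can be read together, with most such subjects staying in the study. The Protocol is silent on later data; it does not forbid collecting them, and events before withdrawal remain recorded. Sections 5.1 and 5.1.2 run adverse event recording to the last follow-up or final scheduled visit, without saying how that applies to someone already withdrawn. This makes the loss conditional, but it leaves the decision to site discretion.

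**The entry criteria lower the frequency.** Exclusions 3, 5, 8 and 18 cover expected cardiac surgery within a year, expected PCI within 30 days, and anticipated CRT or a left ventricular assist device within 12 months. That stands. Unanticipated CRT, later PCI and transplant remain possible.

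**Sensitivity analyses are planned.** Last observation carried forward on ITT (SAP 2.4.2) restores a withdrawn subject, but with a value usually taken before the intervention. The mixed model (SAP 2.1.3) uses the same truncated data. Exit reasons by treatment group (SAP 2.4.1.1) show the loss without repairing it. The mitigation is partial.

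**Stronger readings.** A reader might infer that ITT turns into the per-protocol comparison. It does not: non-implanted Treatment subjects stay in ITT, and per-protocol has further exclusions for unblinding, eligibility and visit windows. A reader might also infer that 6.2 breaks an unconditional promise. The same paragraph openly states the complete-case rule, and the group it expressly keeps is the non-implanted one. Finally, a reader might take the CRT reduction from 36 to 25 ml cited in 6.6 and apply it to 5% to 20% of Controls, giving 0.55 to 2.2 ml in the device's favour. That sets the Treatment rate to zero and borrows a before-after change from CRT candidates, although anticipated CRT is excluded here. It also ignores that deteriorating subjects could have a positive x.

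**Conclusion.** The concern holds in limited form. Optional withdrawal after a confounding intervention, no stated data collection afterwards, and a complete-case primary analysis can together remove such subjects selectively from ITT and from later safety follow-up. On this one criterion ITT moves closer to per-protocol, while Protocol 6.2 and SAP 2.3.3 treat the same event only as a per-protocol matter.

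Over the assumed range the effect on the primary estimate is 0 to 1.5 ml, and its direction is unknown. It rests on assumed rates, an assumed x common to both arms, and withdrawal of every subject counted in pC and pT. The required sample size is unaffected. Because data that were never collected cannot be recovered at analysis, this is a cheap improvement worth making.

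**What to change.** - Remove confounding intervention as a reason for withdrawal from the study in Protocol 3.8.6.1. This concerns data collection only, not clinical care.
- State that these subjects continue scheduled follow-up to 12 months unless they withdraw consent: echo where the native valve can be measured, walk test, major adverse events, heart failure hospitalization and survival.
- Define the term, record the type and date of each intervention on the case report form, and report them by arm.
- Exclude these subjects from the per-protocol set only.
- Prespecify in the SAP how death and transplant are handled in the regurgitant volume analysis.

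The visits are already in the schedule. The cost is a protocol amendment, which under Protocol 7.5 needs Executive Committee review and ethics and regulatory approval, plus the added form fields. The ITT estimate may become somewhat more variable.

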3.8.6.2 Procedures for Reporting Subjects Missing Follow-Up

As soon as it has been determined that a subject has missed a scheduled follow-up examination, the Cardiac Dimensions clinical study monitor must be notified by telephone, e-mail, or facsimile. The study coordinator should attempt to contact the subject at least three times after each missed visit and one of these attempts should be by certified mail with signature confirmation. The subject should not be considered lost-to-follow-up until all attempts to contact the subject have failed.

3.8.6.3 Data Collection and Follow-up for Withdrawn Subjects

If a subject withdraws consent to participate in the study, attempts should be made to obtain permission to record survival data through the 1-year follow-up period.

3.8.7 Cross-Over Registry

Study subjects randomized to the Control group will be offered the option of receiving the investigational device after completing their 1-year follow-up if they continue to meet all of the study eligibility criteria.

Cross-Over registry subjects will be followed at discharge and for 30-days post the CARILLON procedure. The discharge and 30-day-up assessments will be identical to those collected in the randomized portion of the trial (see Sections 3.7.3.1 and 0). On completion of the 30-day follow-up the Cross-Over registry subjects will be exited from the study.

4 Blinding

4.1 Double-Blind Study

This will be a double-blind study in order to reduce the effect of bias and potential placebo effect on specific primary and/or secondary endpoint assessments. A double-blind is a type of masking in which two or more parties involved with the clinical trial do not know which participants have been assigned which interventions. All study subjects and any study personnel responsible for primary efficacy and/or select secondary endpoint assessments (reference section 4.1.1) will be blinded as to whether subjects are in the Treatment group or the Control group. Blinding will be maintained through the 12 month follow-up. All study personnel will be trained to follow study blinding procedures to ensure maintenance of the study blind. Subjects will be continually reminded that adhering to the blinding procedures is a critical part of their involvement in the study.

4.1.1 Blinded Assessments

The following study-related assessments require the assessor to be blinded to the treatment assignment:

- Six minute walk test (6MWT)
 - 6MWT administrator
- All echocardiographic mitral regurgitation and LV hemodynamic parameters
 - Echo corelab assessor
- New York Heart Association (NYHA) classification
 - NYHA assessor
- Kansas City Cardiomyopathy Questionnaire (KCCQ)
 - KCCQ administrator
- SF-12 QoL Questionnaire (SF-12)
 - SF-12 administrator

